14 STUDY OVERSIGHT AND DATA REPORTING / REGULATORY REQUIREMENTS

Adverse event lists, guidelines, and instructions for AE reporting can be found in Section 10 (Adverse Events: List and Reporting Requirements).

14.1 Study Oversight

This protocol is monitored at several levels, as described in this section. The Protocol Principal Investigator is responsible for monitoring the conduct and progress of the clinical trial, including the ongoing review of accrual, patient-specific clinical and laboratory data, and routine and serious adverse events; reporting of expedited adverse events; and accumulation of reported adverse events from other trials testing the same drug(s). The Protocol Principal Investigator and statistician have access to the data at all times through the CTMS web-based reporting portal.

All Study Investigators at participating sites who register/enroll patients on a given protocol are responsible for timely submission of data via Medidata Rave and timely reporting of adverse events for that particular study. This includes timely review of data collected on the electronic CRFs submitted via Medidata Rave.

All studies are also reviewed in accordance with the enrolling institution’s data safety monitoring plan.

14.2 Data Reporting

Medidata Rave is a clinical data management system being used for data collection for this trial/study. Access to the trial in Rave is controlled through the CTEP-IAM system and role assignments. To access Rave via iMedidata:

- Site staff will need to be registered with CTEP and have a valid and active CTEP-IAM account, and
- Assigned one of the following Rave roles on the relevant Lead Protocol Organization (LPO) or Participating Organization roster at the enrolling site: Rave CRA, Rave Read Only, Rave CRA (LabAdmin), Rave SLA, or Rave Investigator. Refer to <https://ctep.cancer.gov/investigatorResources/default.htm> for registration types and documentation required.
 - To hold Rave CRA or Rave CRA (Lab Admin) role, site staff must hold a minimum of an AP registration type,
 - To hold Rave Investigator role, the individual must be registered as an NPIVR or IVR, and
 - To hold Rave Read Only role, site staff must hold an Associates (A) registration type.

If the study has a DTL, individuals requiring write access to Rave must also be assigned the appropriate Rave tasks on the DTL.

Upon initial site registration approval for the study in Regulatory Support System (RSS), all persons with Rave roles assigned on the appropriate roster will be sent a study invitation e-mail from iMedidata. To accept the invitation, site staff must log in to the Select Login (<https://login.imedidata.com/selectlogin>) using their CTEP-IAM username and password, and click on the *accept* link in the upper right-corner of the iMedidata page. Site staff will not be able to access the study in Rave until all required Medidata and study specific trainings are completed. Trainings will be in the form of electronic learnings (eLearnings), and can be accessed by clicking on the link in the upper right pane of the iMedidata screen. If an eLearning is required and has not yet been taken, the link to the eLearning will appear under the study name in iMedidata instead of the *Rave EDC* link; once the successful completion of the eLearning has been recorded, access to the study in Rave will be granted, and a *Rave EDC* link will display under the study name.

Site staff that have not previously activated their iMedidata/Rave account at the time of initial site registration approval for the study in RSS will also receive a separate invitation from iMedidata to activate their account. Account activation instructions are located on the CTSU website in the Rave section under the Rave resource materials (Medidata Account Activation and Study Invitation Acceptance). Additional information on iMedidata/Rave is available on the CTSU members' website in the Data Management > Rave section at www.ctsu.org/RAVE/ or by contacting the CTSU Help Desk at [name] or by e-mail at [contact].

14.2.1 Method

This study will be monitored by the Clinical Trials Monitoring Service (CTMS). Data will be submitted to CTMS at least once every two weeks via Medidata Rave (or other modality if approved by CTEP). Information on CTMS reporting is available at: <http://www.theradex.com/clinicalTechnologies/?National-Cancer-Institute-NCI-11>. On-site audits will be conducted on an 18-36 month basis as part of routine cancer center site visits.

More frequent audits may be conducted if warranted by accrual or due to concerns regarding data quality or timely submission. For CTMS monitored studies, after users have activated their accounts, please contact the Theradex Help Desk at [contact] or by email at [contact] for additional support with Rave and completion of CRFs.

14.2.2 Responsibility for Data Submission

For ETCTN trials, it is the responsibility of the PI(s) at the site to ensure that all investigators at the ETCTN Sites understand the procedures for data submission for each ETCTN protocol and that protocol specified data are submitted accurately and in a timely manner to the CTMS via the electronic data capture system, Medidata Rave.

Data are to be submitted via Medidata Rave to CTMS on a real-time basis, but no less than once every 2 weeks. The timeliness of data submissions and timeliness in resolving data queries will be tracked by CTMS. Metrics for timeliness will be followed and assessed on a quarterly basis. For the purpose of Institutional Performance Monitoring, data will be considered delinquent if it is greater than 4 weeks past due.

Data from Medidata Rave and CTEP-AERS is reviewed by the CTMS on an ongoing basis as data is received. Queries will be issued by CTMS directly within Rave. The queries will appear on the Task Summary Tab within Rave for the CRA at the ETCTN to resolve. Monthly web-based reports are posted for review by the Drug Monitors in the IDB, CTEP. Onsite audits will be conducted by the CTMS to ensure compliance with regulatory requirements, GCP, and NCI policies and procedures with the overarching goal of ensuring the integrity of data generated from NCI-sponsored clinical trials, as described in the ETCTN Program Guidelines, which may be found on the CTEP (http://ctep.cancer.gov/protocolDevelopment/electronic_applications/adverse_events.htm) and CTSU websites.

CTMS will utilize a core set of eCRFs that are Cancer Data Standards Registry and Repository (caDSR) compliant (<http://cbiit.nci.nih.gov/ncip/biomedical-informatics-resources interoperability-and-semantics/metadata-and-models>). Customized eCRFs will be included when appropriate to meet unique study requirements. The PI is encouraged to review the eCRFs, working closely with CTMS to ensure prospectively that all required items are appropriately captured in the eCRFs prior to study activation. CTMS will prepare the eCRFs with built-in edit checks to the extent possible to promote data integrity.

CDUS data submissions for ETCTN trials activated after March 1, 2014, will be carried out by the CTMS contractor, Theradex. CDUS submissions are performed by Theradex on a monthly basis. The trial's lead institution is responsible for timely submission to CTMS via Rave, as above.

Further information on data submission procedures can be found in the ETCTN Program Guidelines (http://ctep.cancer.gov/protocolDevelopment/electronic_applications/adverse_events.htm).

14.3 Data Quality Portal

The Data Quality Portal (DQP) provides a central location for site staff to manage unanswered queries and form delinquencies, monitor data quality and timeliness, generate reports, and review metrics.

The DQP is located on the CTSU members' website under Data Management. The Rave Home section displays a table providing summary counts of Total Delinquencies and Total Queries. DQP Queries, DQP Delinquent Forms, and the DQP Reports modules are available to access details and reports of unanswered queries, delinquent forms, and timeliness reports. Review the DQP modules on a regular basis to manage specified queries and delinquent forms.

The DQP is accessible by site staff that are rostered to a site and have access to the CTSU website. Staff that have Rave study access can access the Rave study data using a direct link on the DQP.

To learn more about DQP use and access, click on the Help icon displayed on the Rave Home, DQP Queries, and DQP Delinquent Forms modules.

Note: Some Rave protocols may not have delinquent form details or reports specified on the DQP. A protocol must have the Calendar functionality implemented in Rave by the Lead Protocol Organization (LPO) for delinquent form details and reports to be available on the DQP. Site staff should contact the LPO Data Manager for their protocol regarding questions about Rave Calendaring functionality.

14.4 Collaborative Agreements Language

The agent(s) supplied by CTEP, DCTD, NCI used in this protocol is/are provided to the NCI under a Collaborative Agreement (CRADA, CTA, CSA) between the Pharmaceutical Company(ies) (hereinafter referred to as "Collaborator(s)") and the NCI Division of Cancer Treatment and Diagnosis. Therefore, the following obligations/guidelines, in addition to the provisions in the "Intellectual Property Option to Collaborator" (http://ctep.cancer.gov/industryCollaborations2/intellectual_property.htm) contained within the terms of award, apply to the use of the Agent(s) in this study:

- 14.4.1 Agent(s) may not be used for any purpose outside the scope of this protocol, nor can Agent(s) be transferred or licensed to any party not participating in the clinical study. Collaborator(s) data for Agent(s) are confidential and proprietary to Collaborator(s) and shall be maintained as such by the investigators. The protocol documents for studies utilizing Agents contain confidential information and should not be shared or distributed without the permission of the NCI. If a copy of this protocol is requested by a patient or patient's family member participating on the study, the individual should sign a confidentiality agreement. A suitable model agreement can be downloaded from: <http://ctep.cancer.gov>.

- 14.4.2 For a clinical protocol where there is an investigational Agent used in combination with (an)other Agent(s), each the subject of different Collaborative Agreements, the access to and use of data by each Collaborator shall be as follows (data pertaining to such combination use shall hereinafter be referred to as "Multi-Party Data"):
- 14.4.2.1 NCI will provide all Collaborators with prior written notice regarding the existence and nature of any agreements governing their collaboration with NCI, the design of the proposed combination protocol, and the existence of any obligations that would tend to restrict NCI's participation in the proposed combination protocol.
 - 14.4.2.2 Each Collaborator shall agree to permit use of the Multi-Party Data from the clinical trial by any other Collaborator solely to the extent necessary to allow said other Collaborator to develop, obtain regulatory approval or commercialize its own Agent.
 - 14.4.2.3 Any Collaborator having the right to use the Multi-Party Data from these trials must agree in writing prior to the commencement of the trials that it will use the Multi-Party Data solely for development, regulatory approval, and commercialization of its own Agent.
- 14.4.3 Clinical Trial Data and Results and Raw Data developed under a Collaborative Agreement will be made available to Collaborator(s), the NCI, and the FDA, as appropriate and unless additional disclosure is required by law or court order as described in the IP Option to Collaborator (http://ctep.cancer.gov/industryCollaborations2/intellectual_property.htm). Additionally, all Clinical Data and Results and Raw Data will be collected, used and disclosed consistent with all applicable federal statutes and regulations for the protection of human subjects, including, if applicable, the *Standards for Privacy of Individually Identifiable Health Information* set forth in 45 C.F.R. Part 164.
- 14.4.4 When a Collaborator wishes to initiate a data request, the request should first be sent to the NCI, who will then notify the appropriate investigators (Group Chair for Cooperative Group studies, or PI for other studies) of Collaborator's wish to contact them.
- 14.4.5 Any data provided to Collaborator(s) for Phase 3 studies must be in accordance with the guidelines and policies of the responsible Data Monitoring Committee (DMC), if there is a DMC for this clinical trial.
- 14.4.6 Any manuscripts reporting the results of this clinical trial must be provided to CTEP by the Group office for Cooperative Group studies or by the principal investigator for non- Cooperative Group studies for immediate delivery to Collaborator(s) for advisory review and comment prior to submission for publication. Collaborator(s) will have 30 days from the date of receipt for review. Collaborator shall have the right to

request that publication be delayed for up to an additional 30 days in order to ensure that Collaborator's confidential and proprietary data, in addition to Collaborator(s)'s intellectual property rights, are protected. Copies of abstracts must be provided to CTEP for forwarding to Collaborator(s) for courtesy review as soon as possible and preferably at least three (3) days prior to submission, but in any case, prior to presentation at the meeting or publication in the proceedings. Press releases and other media presentations must also be forwarded to CTEP prior to release.

Copies of any manuscript, abstract and/or press release/ media presentation should be sent to:

Email: [contact]

The Regulatory Affairs Branch will then distribute them to Collaborator(s). No publication, manuscript or other form of public disclosure shall contain any of Collaborator's confidential/proprietary information.

14.5 Genomic Data Sharing Plan

The investigators and statistician and/or bioinformaticians for a study will have access to all data on mutations and variants stored in the Theradex Data Base and the GDC. This information will be sequestered from access throughout the study until it is analyzed for purposes of reporting and publishing of the study results. As specified in the CRADA for the agents used in the clinical study, the pharmaceutical collaborator will have at least 6 months, longer if needed for a regulatory filing, to review the data and or receive copies of the data once the study is completed and analyzed, or sooner, if specified for purposes of generating Intellectual Property. Once these timeframes have been exceeded, the data will be available through a Data Access Committee (DAC) in the GDC following NCI and Collaborator review of the proposals.

14.6 Incidental/Secondary Findings Disclosure Procedure

Given the potential clinical implications conferred by detecting a germline and/or somatic mutation in one of the proven cancer susceptibility genes, this protocol will use the following disclosure procedure, consistent with the recommendations of the American College of Medical and Genomics (ACMG) (Green *et al.*, 2013 and Kalia *et al.*, 2016):

The NCI Molecular Characterization Laboratory will review the mutations/variants once at the time of initial specimen evaluation according to the most recent version of the ACMG guidance on variants. The NCI Molecular Characterization Laboratory will not re-review all specimens received if a new version of the ACMG guidance is published after the initial review.

For each participant with a pathogenic or likely pathogenic germline and/or somatic variant detected in the WES of blood (as defined in the ACMG guidance), the NCI Molecular Characterization Laboratory will report to the Program Director or Scientific Officer the UPID and variant(s) identified. The Program Director or Scientific Officer will contact Theradex to obtain the name of the protocol, investigator treating the patient, and the Principal Investigator of the grant. The treating physician will be contacted by phone and in writing to ask the patient whether he or she is interested in learning more about the finding.

If the patient wants to know more, the physician should contact the Program Director for more information about the mutation/variant. The treating physician and a medical genetics counselor should meet with the patient to discuss the importance and meaning of the finding, but not the finding itself, and notify the patient that this research finding must be confirmed by Sanger sequencing at the patient's/patient insurer's expense in a Clinical Laboratory Improvement Amendments (CLIA)-approved laboratory. The treating physician and genetic counselor should inform the patient of the confirmed result and its meaning and significance to the patient. If desired, the patient may elect to undergo genetic counseling and confirmatory CLIA-approved clinical testing on his or her own. Neither the research laboratory nor the National Cancer Institute will be responsible for the costs incurred for any confirmatory genetic testing or counseling.

APPENDIX A PERFORMANCE STATUS CRITERIA

ECOG Performance Status Scale			
Grade	Descriptions		
0	Normal activity. Fully active, able to carry on all pre-disease performance without restriction.		
1	Symptoms, but ambulatory. Restricted in physically strenuous activity, but ambulatory and able to carry out work of a light or sedentary nature (e.g., light housework, office work).		
2	In bed <50% of the time. Ambulatory and capable of all self-care, but unable to carry out any work activities. Up and about more than 50% of waking hours.		
3	In bed >50% of the time. Capable of only limited self-care, confined to bed or chair more than 50% of waking hours.		
4	100% bedridden. Completely disabled. Cannot carry on any self-care. Totally confined to bed or chair.		
5	Dead.		

APPENDIX B FORMULA TO ESTIMATE RENAL FUNCTION USING SERUM CREATININE

Formulas to estimate renal function using serum creatinine provided by the NCI’s Investigational Drug Steering Committee (IDSC) Pharmacological Task Force in table below.

1. Estimated glomerular filtration rate (eGFR) using the Chronic Kidney Disease Epidemiology Collaboration (CKD-EPI) (Levey *et al.*, 2009).

Formulae:

Race and Sex	Serum Creatinine (SCr), $\mu\text{mol/L}$ (mg/dL)	Equation
Black	Female ≤ 62 (≤ 0.7)	$\text{GFR} = 166 \times (\text{SCr}/0.7)^{-0.329} \times (0.993)^{\text{Age}}$
	Female > 62 (> 0.7)	$\text{GFR} = 166 \times (\text{SCr}/0.7)^{-1.209} \times (0.993)^{\text{Age}}$
	Male ≤ 80 (≤ 0.9)	$\text{GFR} = 163 \times (\text{SCr}/0.9)^{-0.411} \times (0.993)^{\text{Age}}$
	Male > 80 (> 0.9)	$\text{GFR} = 163 \times (\text{SCr}/0.9)^{-1.209} \times (0.993)^{\text{Age}}$
White or other	Female ≤ 62 (≤ 0.7)	$\text{GFR} = 144 \times (\text{SCr}/0.7)^{-0.329} \times (0.993)^{\text{Age}}$
	Female > 62 (> 0.7)	$\text{GFR} = 144 \times (\text{SCr}/0.7)^{-1.209} \times (0.993)^{\text{Age}}$
	Male ≤ 80 (≤ 0.9)	$\text{GFR} = 141 \times (\text{SCr}/0.9)^{-0.411} \times (0.993)^{\text{Age}}$
	Male > 80 (> 0.9)	$\text{GFR} = 141 \times (\text{SCr}/0.9)^{-1.209} \times (0.993)^{\text{Age}}$

SCr in mg/dL; Output is in mL/min/1.73 m² and needs no further conversions.

2. eGFR using the Modification of Diet in Renal Disease (MDRD) Study (Levey *et al.*, 2006).

$175 \times \text{SCr}^{-1.154} \times \text{age}^{-0.203} \times 0.742$ (if female) $\times 1.212$ (if black)

Output is in mL/min/1.73 m² and needs no further conversions.

3. Estimated creatinine clearance (CLCr) by the Cockcroft-Gault (C-G) equation (Cockcroft and Gault, 1976).

$$\text{CLCr (mL/min)} = \frac{[140 - \text{age (years)}] \times \text{weight (kg)}}{72 \times \text{serum creatinine (mg/dL)}} \{ \times 0.85 \text{ for female patients} \}$$

Followed by conversion to a value normalized to 1.73 m² with the patient’s body surface area (BSA).

References

1. Levey, A.S., L.A. Stevens, C.H. Schmid, *et al.* (2009). A new equation to estimate glomerular filtration rate. *Ann Intern Med.* 150:604-612.
2. Levey, A.S., J. Coresh, T. Greene, *et al.* (2006). Using standardized serum creatinine values in the modification of diet in renal disease study equation for estimating glomerular filtration rate. *Ann Intern Med.* 145:247-254.

APPENDIX C PATIENT CLINICAL TRIAL WALLET CARD

 NATIONAL CANCER INSTITUTE
CLINICAL TRIAL WALLET CARD
Show this card to all of your healthcare providers and keep it with you in case you go to the emergencyroom.
Patient Name:
Diagnosis:
Study Doctor:
Study Doctor Phone #:
NCI Trial #: 10300
Study Drug(S): Pembrolizumab (MK-3475), cytarabine, and either daunorubicin or idarubicin
For more information: [name] cancer.gov clinicaltrials.gov

APPENDIX D RESPONSE CRITERIA (PER ELN 2017 RECOMMENDATIONS)

Response criteria in AML

Response

CR without minimal residual disease (CRM RD-) If studied pretreatment, CR with negativity for a genetic marker by RT-qPCR, or CR with negativity by MFC

Complete remission (CR): Bone marrow blasts <5%; absence of circulating blasts and blasts with Auer rods; absence of extramedullary disease; ANC $\geq 1.0 \times 10^9/L$ (1000/ μL); platelet count $\geq 100 \times 10^9/L$ (100 000/ μL); MRD+ or unknown

CR with incomplete count recovery (CRi): All CR criteria except for residual neutropenia ($< 1.0 \times 10^9/L$ [1000/ μL]) or thrombocytopenia ($< 100 \times 10^9/L$ [100 000/ μL])

CR with incomplete hematologic recovery (CRh): All CR criteria with neutrophil count ($> 0.5 \times 10^9/L$ [1000/ μL]) and platelet count ($> 50 \times 10^9/L$ [100 000/ μL])

Morphologic leukemia-free state (MLFS): Bone marrow blasts <5%; absence of blasts with Auer rods; absence of extramedullary disease; no hematologic recovery required. (Marrow should not merely be “aplastic”; at least 200 cells should be enumerated or cellularity should be at least 10%)

Partial remission (PR) All hematologic criteria of CR; decrease of bone marrow blast percentage to 5% to 25%; and decrease of pretreatment bone marrow blast percentage by at least 50%

Treatment failure

Primary refractory disease: No CR or CRi after 2 courses of intensive induction treatment; excluding patients with death in aplasia or death due to indeterminate cause

Death in aplasia: Deaths occurring ≥ 7 d following completion of initial treatment while cytopenic; with an aplastic or hypoplastic bone marrow obtained within 7 d of death, without evidence of persistent leukemia

Death from indeterminate cause: Deaths occurring before completion of therapy, or < 7 d following its completion; or deaths occurring ≥ 7 d following completion of initial therapy with no blasts in the blood, but no bone marrow examination available

Response criteria for clinical trials

Stable disease: Absence of CRM RD-, CR, CRi, PR, MLFS; and criteria for PD not met Period of stable disease should last at least 3 months

Progressive disease (PD): Evidence for an increase in bone marrow blast percentage and/or

increase of absolute blast counts in the blood

- >50% increase in marrow blasts over baseline (a minimum 15% point increase is required in cases with <30% blasts at baseline; or persistent marrow blast percentage of >70% over at least 3 mo; without at least a 100% improvement in ANC to an absolute level ($>0.5 \times 10^9/L$ [$500/\mu L$], and/or platelet count to $>50 \times 10^9/L$ [$50\,000/\mu L$] nontransfused)
- >50% increase in peripheral blasts (WBC \times % blasts) to $>25 \times 10^9/L$ ($>25\,000/\mu L$) (in the absence of differentiation syndrome)
- New extramedullary disease Some protocols may allow transient addition of hydroxyurea to lower blast counts

“Progressive disease” is usually accompanied by a decline in ANC and platelets and increased transfusion requirement and decline in performance status or increase in symptoms

Relapse

Hematologic relapse (after CRMRD⁻, CR, CRi) Bone marrow blasts $\geq 5\%$; or reappearance of blasts in the blood; or development of extramedullary disease

Molecular relapse (after CRMRD⁻) If studied pretreatment, reoccurrence of MRD as assessed by RT-qPCR or by MFC

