10.4 Analysis of Secondary and Exploratory Endpoints

10.4.1 Secondary Endpoints

10.4.1.1 Efficacy Endpoints:

- Assess the rate of CR/CRi as defined per the ELN 2017 (see Appendix D) response criteria at time of count recovery after induction therapy with chemotherapy + Pembrolizumab (MK-3475).
- Assess MRD negativity at Day 14.
- Assess the rate of MRD-negative CR at end of induction therapy.
- Assess the rate of MRD-negative CR at end of consolidation.
- Assess rates of complete remission with partial recovery count (CRh) and Hematologic improvement (HI) to red blood cells and platelets.
- Assess the percentage of patients with MRD-CR at time of count recovery after first cycle of consolidation therapy using a MRD cut-off of 0.01%.
- Assess EFS, RFS, calculated as the time from initial treatment to either disease relapse or death.
- Assess the DOR (defined as the time from first CR to the date of the first documented relapse or death, whichever occurs first) and OS.

10.4.1.2 Safety Endpoints:

- Assess safety endpoints including proportion of patients who develop severe toxicity.

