10.5.2 Evaluation of Response

All patients who were randomized must be assessed for response to treatment, even if there are major protocol treatment deviations or if they are ineligible. Each patient will be assigned one of the accepted ELN2017 response categories (see Appendix D). [Note: By arbitrary convention, category 9 usually designates the “unknown” status of any type of data in a clinical database.]

All patients who were randomized (with the possible exception of those who received no study medication) should be included in the main analysis of the response rate. Patients who do not achieve CR/CRi after induction and first consolidation will be considered to have a treatment failure. Thus, an incorrect treatment schedule or drug administration does not result in exclusion from the analysis of the response rate.

All conclusions should be based on all eligible patients. Sub-analyses may then be performed on the basis of a subset of patients, excluding those for whom major protocol deviations have been identified (*e.g.*, early death due to other reasons, early discontinuation of treatment, major protocol violations, *etc.*). However, these sub-analyses may not serve as the basis for drawing conclusions concerning treatment efficacy, and the reasons for excluding patients from the analysis should be clearly reported. The 95% confidence intervals should also be provided.

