13.2 Hematologic Response

13.2.1 Complete Response (CR) without minimal residual disease (CRM RD-): If studied pretreatment, CR with negativity for a genetic marker by RT-qPCR, or CR with negativity by MFC

13.2.2 Complete remission (CR): Bone marrow blasts <5%; absence of circulating blasts and blasts with Auer rods; absence of extramedullary disease; ANC $\geq 1.0 \times 10^9/L$ (1000/ μ L); platelet count $\geq 100 \times 10^9/L$ (100 000/ μ L); MRD+ or unknown

13.2.3 CR with incomplete count recovery (CRi): All CR criteria except for residual neutropenia ($< 1.0 \times 10^9/L$ [1000/ μ L]) or thrombocytopenia ($< 100 \times 10^9/L$ [100,000/ μ L])

13.2.4 CR with partial recovery count (CRh): All CR criteria with neutrophil count $\geq 0.5 \times 10^9/L$ and platelet count $\geq 50 \times 10^9/L$. *CRh is being recorded as a separate response criteria from other responses (for example patient could have CRi by traditional criteria but also CRh).*

13.2.5 Hematologic improvement: Erythroid response (E) (pretreatment Hgb < 11 g/dL) Hgb increase by ≥ 1.5 g/dL, Platelet response (P) (pretreatment platelets $< 100 \times 10^9/L$) Absolute increase of $\geq 30 \times 10^9/L$ for patients starting with $> 20 \times 10^9/L$ platelets Increase from $< 20 \times 10^9/L$ to $> 20 \times 10^9/L$ and by at least 100%.

13.2.6 **Morphologic leukemia-free state (MLFS):** Bone marrow blasts <5%; absence of blasts with Auer rods; absence of extramedullary disease; no hematologic recovery required. (Marrow should not merely be “aplastic”; at least 200 cells should be enumerated or cellularity should be at least 10%)

13.2.7 **Partial remission (PR)** All hematologic criteria of CR; decrease of bone marrow blast percentage to 5% to 25%; and decrease of pretreatment bone marrow blast percentage by at least 50%

Peripheral Blood Counts:

- Neutrophil count $\geq 1.0 \times 10^9/L$.
- Platelet count $\geq 100 \times 10^9/L$.
- Reduced hemoglobin concentration or hematocrit has no bearing on remission status.
- Leukemic blasts must not be present in the peripheral blood.

Bone Marrow Aspirate and Biopsy:

- Cellularity of bone marrow biopsy must be >20% with maturation of all cell lines.
- <5% blasts
- Auer rods must not be detectable.

Extramedullary leukemia, such as CNS or soft tissue involvement, must not be present.

13.2.8 **Stable disease:** Absence of CRMRD–, CR, CRi, PR, MLFS; and criteria for PD not met.

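### The CRh entry in Appendix D contradicts itself: its bracketed per-microlitre counts are twice the stated thresholds and equal the CR cut-offs

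*Combined protocol and SAP*

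**What the plan says.** CRh is a named secondary endpoint: Section 10.4.1.1 lists "Assess rates of complete remission with partial recovery count (CRh"), and objective 1.2.2 says the same. The protocol defines the category twice.

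- Appendix D has an entry that begins "CR with incomplete hematologic recovery (CRh): All CR criteria with neutrophil count". It gives the neutrophil criterion as "All CR criteria with neutrophil count ($> 0.5 \times 10^9/L$ [1000" per µL and the platelet criterion as "platelet count ($> 50 \times 10^9/L$ [100 000" per µL.
- Section 13.2.4 gives at least 0.5 x10^9/L and at least 50 x10^9/L, with no per-microlitre figures. It adds that "CRh is being recorded as a separate response criteria from other responses" and allows a patient to hold both CRi and CRh.

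For CR, Appendix D requires "ANC $\geq 1.0 \times 10^9/L$ (1000" per µL and "platelet count $\geq 100 \times 10^9/L$ (100 000" per µL.

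On which text assessors should use, Section 10.5.2 says "Each patient will be assigned one of the accepted ELN2017 response categories (see Appendix D"). Section 13.1 instead refers to the definitions that follow it, which are those in Section 13.2.

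**The concern.** A threshold given in two units must be the same threshold in both, and here it is not. The per-microlitre figures in the CRh entry are the ones that define full count recovery for CR. Many laboratories report counts per microlitre, so the bracketed figure is the one a site might well read off. Section 10.5.2 also names this appendix for assigning response.

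What is at stake is the CRh rate. If some sites used the bracketed figures and others the x10^9/L figures or Section 13.2.4, patients with the same counts would be classified differently. With 25 patients per arm, each patient moved in or out of CRh changes that arm's rate by 1/25 = 4 percentage points.

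**Working it through.** **Inputs.** CRh, CR and progressive-disease entries of Appendix D; Section 13.2.4.

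**Conversion.** One litre is 10^6 µL, so x times 10^9 per litre equals x × 10^9 / 10^6 = x × 1000 per µL.

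| Entry | Stated x10^9/L | Stated per µL | Computed per µL | Agrees? |
|---|---|---|---|---|
| CR, neutrophils | 1.0 | 1000 | 1.0 × 1000 = 1000 | yes |
| CR, platelets | 100 | 100 000 | 100 × 1000 = 100 000 | yes |
| Progressive disease, neutrophils | 0.5 | 500 | 0.5 × 1000 = 500 | yes |
| Progressive disease, platelets | 50 | 50 000 | 50 × 1000 = 50 000 | yes |
| CRh, neutrophils | 0.5 | 1000 | 0.5 × 1000 = 500 | no: 1000/500 = 2 |
| CRh, platelets | 50 | 100 000 | 50 × 1000 = 50 000 | no: 100 000/50 000 = 2 |

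The appendix's other conversions reproduce; only the CRh pair fails. The failing brackets are the same figures as in the CRi line directly above. A carry-over is plausible, but that is an inference.

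**Effect on classification.** Take patients who meet every other CR criterion and apply each rule to the counts (per µL).

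| Neutrophils | Platelets | CR | CRh, 13.2.4 (≥500, ≥50 000) | CRh, Appendix D in x10^9/L (>500, >50 000) | CRh, Appendix D brackets (>1000, >100 000) |
|---|---|---|---|---|---|
| 700 | 75 000 | no | yes | yes | no |
| 2000 | 75 000 | no | yes | yes | no |
| 700 | 30 000 | no | no | no | no |
| 500 | 75 000 | no | yes | no | no |
| 1000 | 200 000 | yes | yes | yes | no |
| 2000 | 200 000 | yes | yes | yes | yes |

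- Rows 1 and 2 are the affected patients: above both CRh floors, with at least one count below the CR cut-off. The brackets remove them from CRh.
- Row 3 has a neutrophil count in the 500-999 range but is not CRh under any rule, because CRh needs both floors.
- Row 4 shows a second, smaller mismatch: Appendix D uses > and Section 13.2.4 uses ≥, so they disagree when a count sits exactly on a floor.
- Row 5 shows that the bracketed rule and CR still differ at exact equality, because CR uses ≥.

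In general, any patient with neutrophils above 1000 and platelets above 100 000 also satisfies the CR count criteria. Under the brackets, then, CRh without CR is impossible.

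**The case against.** The strongest reply is that the intended definition is easy to recover. Section 13.2.4 states it with no conflicting brackets, and Section 13.1 sends response classification to that part of the protocol. The wording of the secondary endpoint is closer to the name in Section 13.2.4 than to the name in Appendix D. In Section 10.4.1.1 the pointer to Appendix D is attached to the CR/CRi item, not the CRh item. Neutrophil and platelet counts are collected, so CRh can be derived from them whatever a site ticked. CRh plays no part in the primary endpoint or in the rules for moving between treatment phases, which use CR/CRi. All of this stands, and it is why the point is minor.

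It does not clear the entry. Section 10.5.2 still cites Appendix D for assigning response, and no reading of the CRh line satisfies both of its figures. A PDF-reading fault is unlikely, since the neighbouring entries came through correctly and the wrong values are whole, legible numbers.

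Three stronger readings are tempting, and the documents do not support them.

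- A reader might infer that the CRh endpoint is identical to CR. That follows only if a site prefers the brackets to the x10^9/L figures beside them and to Section 13.2.4, and even then the two differ at exact equality.
- A reader might infer that every patient with neutrophils of 500-1000/µL or platelets of 50 000-100 000/µL would be misclassified. CRh needs both floors and all other CR criteria, so many such patients are unaffected, as row 3 of the second table shows.
- A reader might infer that Section 13.2.4 is faulty because it sets no upper bound, so that CR patients also meet CRh. That section records CRh separately and expressly allows overlap with CRi. CR and CRh can still be counted separately, so restricting the reported rate to patients not in CR would be a reporting preference and not the correction of an error.

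**Conclusion.** The CRh entry in Appendix D is wrong as written: both bracketed conversions are out by a factor of two and coincide with the CR cut-offs. This rests on unit conversion alone and needs no outside source.

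The consequence is conditional. At a site applying the brackets, CRh would lose every patient who meets the other CR criteria, is above both CRh floors, and has neutrophils of 500-999/µL, platelets of 50 000-99 999/µL, or both. How many patients that would be, and whether any site would read the entry that way, cannot be determined from the documents. The primary endpoint of MRD-negative CR/CRi and its stated power of about 71% do not depend on this entry. The severity is minor.

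**What to change.** In the CRh entry of Appendix D, change the brackets to 500/µL and 50 000/µL. In the same edit, make Appendix D and Section 13.2.4 agree on > or ≥ and on one name for the category, since one now calls the recovery incomplete and the other partial. No change is needed to how CRh overlaps with other responses.

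The cost is an edit of a line or two. Design, sample size, treatment and data collection are untouched, and any CRh status already recorded can be checked against the collected counts.
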